Our specific aim is to conduct a pilot study to evaluate the accuracy of continuous glucose monitors (CGM) in End Stage Renal Disease (ESRD) patients on intermittent hemodialysis (iHD). Accuracy will be assessed by calculating the mean absolute relative difference (MARD) between CGM values and concurrent finger stick or venous blood glucose (CBG) in these patients during hemodialysis, and on non-dialysis days.

Primary Hypotheses: The MARD between CGM sensor glucose and CBG will be larger on non-HD days than during dialysis.

Study Design: Biomedical

1. Will controls be used?

Yes – patients are their own controls.

▶ **IF YES, explain the kind of controls to be used.**

Accuracy of CGM during HD session will be compared to the accuracy of the CGM on the same patient when they are not in HD session.

2. What is the study design?

Prospective cohort study using blinded 10-day CGM in 30 ESRD patients on iHD who have a diagnosis of type 1 diabetes mellitus or type 2 diabetes mellitus. Will attempt to recruit approximately 15 participants who use insulin therapy though this is not exclusionary. Patients will be requested to perform finger stick blood glucose (FSBG) values using a study glucometer 7 times daily at home (before meals, 2 hours after meals, and at bedtime) for 10 days. A study team member will obtain approximately 12 blood samples from the existing HD IV line during each (three) HD session the CGM sensor is worn. These blood samples will be immediately processed using the *i-STAT System*. While the goal is to have the subject participate in three hemodialysis sessions, two sessions will be acceptable and not considered a study deviation.

3. Does the study involve a placebo?

No

▶ **IF YES, provide a justification for the use of a placebo**

Human Participants

Ages: 18+

Sex: Any

Race: Any

Subjects- see below

1. Provide target # of subjects (at all sites) needed to complete protocol.

30 subjects

2. Describe expected rate of screen failure/ dropouts/withdrawals from all sites.

40%

3. How many subjects will be enrolled at all sites?

Up to 50 subjects

4. How many subjects will sign a consent form under this UVa protocol?

Up to 50 subjects.

Inclusion/Exclusion Criteria

1. List the criteria for inclusion

- Ages 18+
- Type 1 diabetes mellitus on intermittent HD thrice weekly OR Type 2 diabetes mellitus on intermittent HD thrice weekly
- Willingness and ability to comply with scheduled visits and study procedures

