2. List the criteria for exclusion

- Noncompliant with HD therapies
- Pregnant women
- Subjects with Hct < 30. This will be determined via the monthly blood draw that the subjects coordinate with entry into the study.

3. List any restrictions on use of other drugs or treatments.

- Hydroxyurea - has been known to interfere with current continuous glucose monitor sensors.

Statistical Considerations

1. Is stratification/randomization involved?

No

► IF YES, describe the stratification/ randomization scheme.

► IF YES, who will generate the randomization scheme?

_____ Sponsor

_____ UVa Statistician. Answer/Response:

_____ UVa Investigational Drug Service (IDS)

_____ Other: Answer/Response:

2. What are the statistical considerations for the protocol?

This is a prospective cohort study of 30 patients with diagnosis of Type 1 or Type 2 diabetes mellitus. The patients enrolled in the study will have a blinded CGM placed for 10 days which will measure interstitial glucose using above referenced electroenzymatic technology and record interstitial blood glucose every 5 minutes. The CGM sensor will be collected 10 days after placement of the sensor. The patients will also check venous blood glucose using a provided glucometer seven times daily on non-HD days. During HD sessions, a study team member will measure blood glucose with the use of an *i-STAT System* point of care machine approximately 10-12 times at the following intervals: q15 minutes x 90 minutes, q30 minutes x 60 minutes, then q60 minutes until HD finished. The results from the *i-STAT System* glucose measurements will be recorded in the study flowsheet. The study glucometers will record and store the results of finger stick blood glucose values which will be collected each day (10 days) after placement of the

sensor. The CGM sensors may be discarded by the study subject. CGM transmitters will be returned to the study team. .

The CGM and study glucometer data will be compared in the 30 patients to assess accuracy in between hemodialysis sessions (HD day + 1 [considered euvoletic] and HD day + 2 day [considered volume overloaded]). MARD will be calculated.

3. Provide a justification for the sample size used in this protocol.

This is a small pilot study to assess MARD (accuracy) of CGM in hemodialysis dependent patients with diabetes.

4. What is your plan for primary variable analysis?

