Data scientists at the center for diabetes technology will use CGM, glucometer, and iStat data to calculate the MARD between sensor glucose and venous blood glucose for patients during hemodialysis, and between hemodialysis in different volume states.

5. What is your plan for secondary variable analysis?

Secondary outcomes include duration of HD, volume removed during HD therapy, Basic Metabolic Panel (BMP) prior to HD session including Co2, BUN, glucose, complete blood counts, medications, and daily weight.

6. Have you been working with a statistician in designing this protocol?

No

IF YES, what is their name?

7. Will data from multiple sites be combined during analysis?

No. , Only UVA patients will participate in this study.

7(a). Does the study involve randomization?

IF YES, will randomization be done at each site or among sites?

7(b). Has the sample size calculation considered the variation among sites?

7(c). When combining the data from multiple sites to assess the study results, is the effect of the treatment to be tested (or the association to be tested) assumed to be the same across sites or vary among sites? What is the modelling strategy?

7(d). Is there a common protocol used in all sites?

Study Procedures-Biomedical Research

1. What will be done in this protocol?

Screening (Visit 1):

Potential subjects will be approached during their regularly scheduled dialysis sessions at a UVA dialysis facility. Subjects may be contacted via telephone as well. The subject's provider or study

physician may introduce the study to the potential subject. If interested, a member of the study team will discuss the study in detail and obtain informed consent. Pre-screening inclusion/exclusion questions regarding their possible eligibility for the trial may be reviewed.

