On days that the subject has dialysis, they will attend their regularly scheduled dialysis session and perform that run with no change from standard care. During the session, 10-12 samples (1.5

cc) of blood will be drawn from the HD line that is placed for usual care purposes. These samples will occur at approximately the following times:

0m, 15m, 30m, 45m, 60m, 75m, 90m, 120m, 150m, 210m, then every 60 minutes until the end of the dialysis session.

The blood samples will be used to perform a blood glucose test using an *i-Stat System*. The study team will record results and data obtained clinically for the subjects during this time including lab results (e.g. weekly basic metabolic panel, etc...), dialysis run information (including dextrose concentration of the dialysate), vital signs including height and weight, and other clinically relevant medical information. Estimated blood loss will be 20cc per HD session and 60cc per study period. Glucose values collected during the dialysis session will not be used for treatment purposes.

At Home:

Participants will perform 7 fingerstick blood glucose tests using the study glucometer. These will be done before meals, after meals, and at bedtime. Subjects will be encouraged to use the study glucometer for any additional blood glucose values they wish to perform.

Subjects will weigh themselves every morning upon voiding and record the results in a study record.

While the goal is to have the subject participate in three hemodialysis sessions, two sessions will be acceptable and not considered a study deviation.

Final Study Visit (Day 11)

At the final study visit, subjects will remove the CGM sensor from their abdomen. The sensor will be discarded. The CGM transmitter will be returned to the study team. They will discontinue all use of other study equipment (e.g. study glucometer, scale, etc...) and return all study supplies to the study team. Subjects will continue with their standard care for their end-stage renal disease and diabetes management.

The CGM equipment stores the blood glucose values on the transmitter. The study glucometer will be downloaded by study staff once the subject returns the equipment to the team.

Weigh diaries will be completed.

HSR190012: Evaluation of accuracy of continuous glucose monitoring (CGM) in patients with end stage renal disease (ESRD) on intermittent hemodialysis (iHD).

Fingerstick Schedule for Monday, Wednesday, Friday dialysis patients

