Sensor placement will occur at the conclusion of the patient's Friday dialysis appointment with the following fingerstick schedule:

Friday (Day 1)	Saturday (Day 2)	Sunday (Day 3)	Monday (Day 4)	Tuesday (Day 5)	Wednesday (Day 6)	Thursday (Day 7)	Friday (Day 8)	Saturday (Day 9)	Sunday (Day 10)	Monday (Day 11)
Dialysis day. Place CGM sensor. Check FSBG before meals and at bedtime.	7 FSBG readings: before & after meals & at bedtime.	7 FSBG readings: before & after meals & at bedtime.	Dialysis day. Obtain 10-12 iStat glucose values during HD session: q15m x 90min, q30m x 60min, q60m until end of HD session; 7 FSBG readings: before & after meals & at bedtime	7 FSBG readings: before & after meals & at bedtime.	Dialysis day. Obtain 10-12 iStat glucose values during HD session: q15m x 90min, q30m x 60min, q60m until end of HD session; 7 FSBG readings: before & after meals & at bedtime	7 FSBG readings: before & after meals & at bedtime.	Dialysis day. Obtain 10-12 iStat glucose values during HD session: q15m x 90min, q30m x 60min, q60m until end of HD session; 7 FSBG readings: before & after meals & at bedtime	7 FSBG readings: before & after meals & at bedtime.	7 FSBG readings: before & after meals & at bedtime.	Dialysis day. Final study visit to return study supplies. No FSBGs.

HSR190012: Evaluation of accuracy of continuous glucose monitoring (CGM) in patients with end stage renal disease (ESRD) on intermittent hemodialysis (iHD).

Fingerstick Schedule for Tuesday, Thursday, Saturday dialysis patients

Sensor placement will occur at the conclusion of the patient's Saturday dialysis appointment with the following fingerstick schedule:

Saturday (Day 1)	Sunday (Day 2)	Monday (Day 3)	Tuesday (Day 4)	Wednesday (Day 5)	Thursday (Day 6)	Friday (Day 7)	Saturday (Day 8)	Sunday (Day 9)	Monday (Day 10)	Tuesday (Day 11)

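### Does the during-dialysis MARD need a breakdown by time in session and a rule for the 0-minute reading?

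*Combined protocol and SAP*

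**What the plan says.** - **Study Procedures, Dialysis Days.** The draws taken during the session, 10-12 in number, are scheduled at approximately "0m, 15m, 30m, 45m, 60m, 75m, 90m, 120m, 150m, 210m, then every 60 minutes until the end of the dialysis session".
- **Statistical Considerations, item 2**, gives intervals instead of clock times: "approximately 10-12 times at the following intervals: q15 minutes x 90 minutes, q30 minutes x 60 minutes, then q60 minutes until HD finished". Both fingerstick schedule tables do the same: "Obtain 10-12 iStat glucose values during HD session: q15m x 90min, q30m x 60min, q60m until end of HD session". None of these names a 0-minute draw.
- **Statistical Considerations, item 4.** Analysts will "calculate the MARD between sensor glucose and venous blood glucose for patients during hemodialysis, and between hemodialysis in different volume states". Dialysis is one state here. The only finer division, by volume state, lies between sessions, where item 2 says "The CGM and study glucometer data will be compared in the 30 patients to assess accuracy in between hemodialysis sessions".
- **Objectives/Hypothesis.** The primary hypothesis is that "The MARD between CGM sensor glucose and CBG will be larger on non-HD days than during dialysis".
- **Study Design, item 1**, on controls: "Accuracy of CGM during HD session will be compared to the accuracy of the CGM on the same patient" when that patient is out of session.

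Nothing in the plan places 0m before or after the start of dialysis, says how pairs are weighted, or asks for MARD by elapsed time.

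**The concern.** The during-dialysis MARD is one side of the primary comparison. The Background gives fluid shifts during treatment as a reason sensor accuracy might change, and such shifts can build up over a session. Sampling is dense early and sparse late, so a plain average over readings gives the first 90 minutes more weight than their share of session time. If accuracy moves within the session, one number would not show it and could differ from a time average.

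The 0-minute pair adds a second doubt. It has little or no dialysis exposure, and the interval descriptions do not mention it. Two analysts might treat it differently and each claim to follow the plan.

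**Working it through.** **Inputs.** The draw times come from Dialysis Days. Session length L is not given. I assume 210 to 389 minutes, the range in which the listed times yield the planned 10-12 readings. D, the change in MARD from start to end of session in percentage points, is also not given. Equal weight per pair is a further assumption.

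**Planned count.** Continuing every 60 minutes after 210:

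| L (min) | Readings with 0m | Without 0m | Share at or before 90 min, with 0m |
|---|---|---|---|
| 210-269 | 10 | 9 | 7/10 = 70% |
| 270-329 | 11 | 10 | 7/11 = 64% |
| 330-389 | 12 | 11 | 7/12 = 58% |

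The stated 10-12 is reproduced with 0m counted. At L = 240 the first 90 minutes are 90/240 = 37.5% of the session.

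**Linear change.** The gap between the time average and the average over readings is D × (0.5 − mean(t)/L). At L = 240:
- With 0m: the ten times sum to 795, so the mean is 79.5 and the gap is 0.5 − 79.5/240 = 0.169 × D.
- Without 0m: 795/9 = 88.3, and the gap is 0.5 − 88.3/240 = 0.132 × D.
- Over all L: 0.121-0.206 × D with 0m and 0.079-0.176 × D without. At D = 5 that is 0.6-1.0 and 0.4-0.9 points.

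**Effect of dropping 0m.** mean(t)/L moves by 0.027-0.042, so the measure moves by 0.1-0.2 points at D = 5.

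**Other shapes.**
- Step at 90 minutes: (L − 90)/L minus the share of readings after 90 minutes. At L = 240 with 0m this is 0.625 − 0.300 = 0.325. Over all L it is 0.271-0.365 with 0m and 0.238-0.332 without.
- Fast early change (time constant 15 minutes): 0.086-0.102 with 0m, −0.007 to 0.014 without.
- Mid-session hump, sin(πt/L), L = 240, without 0m: the mean over readings is 0.656 against a time mean of 2/π = 0.637. The average over readings is now further from the early value.

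**End-of-session draw.** The wording about sampling until dialysis ends can be read to include a last sample. At L = 240 this gives (795 + 240)/11 = 94.1, and the linear gap falls to 0.5 − 94.1/240 = 0.108 × D, below the range above. The interval schedule then gives 10 readings without 0m.

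**What a split at 90 minutes could show.** At 210-269 minutes there are 6 readings per session in >0-90 minutes and 3 later. With 30 patients, k sessions each, and assumed SD of the absolute relative difference 8-12 points and within-patient correlation ρ of 0.1-0.5, the 95% half-width of the difference between bands is 1.96 × SD × √[(1 − ρ)(1/(3k) + 1/(6k))/30]:
- k = 3: 0.83 (SD 8, ρ 0.5) to 1.66 (SD 12, ρ 0.1).
- k = 2, which the plan accepts ("two sessions will be acceptable and not considered a study deviation"): 1.01 to 2.04.
- With a further correlation of 0.2 among readings in the same session and band: 1.23 to 2.63 over both cases.

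A linear D separates the bands by 0.40-0.51 × D (at L = 240, (160 − 52.5)/240 = 0.448), so D = 2 gives 0.8-1.0 points. That is at or below nearly all of these half-widths.

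**The case for a change.** The best case for a change is that it would cost only wording. The draws are timed already, so a band summary needs no new data. The protocol states that no statistician helped design it, which argues for writing rules down. Item 1 of Study Design sets in-session accuracy against out-of-session accuracy, and a 0-minute reading lies near that boundary. If accuracy changes within the first quarter of an hour, the 0-minute pair accounts for nearly all of the gap from a time average (0.086-0.102 with it, about zero without).

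Part of this stands: 0m is undefined relative to the start of dialysis, and the arithmetic is right under its assumptions. The rest is weaker.
- The primary hypothesis contrasts dialysis with non-HD days, and a reading at the chair on a dialysis day cannot belong to the latter. The between-session comparison uses the study glucometer, whereas the 0-minute value is an i-STAT result. The pair therefore has no competing home in the main contrast.
- Dialysis Days lists 0m among the samples drawn during the session. Without an end-of-session draw, the 10-reading minimum at 210-269 minutes is reached only with 0m. Excluding it, or calling it pre-dialysis, would reverse the apparent choice and presume a definition that the plan does not give.
- An average that leans towards the early session is not a general result. It depends on equal weighting, no end draw and the shape of the change.

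**Conclusion.** No change is needed. Dense early sampling is not an error, and the plan never promises a time-averaged MARD, so averaging the in-session pairs gives a sound during-dialysis figure for what the protocol calls a small pilot study. The gap from a time average may be zero. Under a linear change it is 0.12-0.21 × D, and under a step at 90 minutes 0.27-0.37 × D, both with 0m included, equal weights, no end draw and an assumed session of 210-389 minutes. The documents give neither the size nor the direction of D, so no bias for or against the hypothesis can be claimed.

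The 0-minute question is a missing detail that analysts can fill sensibly: include the pair as Dialysis Days implies, and show the MARD with and without it if in doubt. Under the linear assumption the two differ by only 0.03-0.04 × D. An early/late summary remains available, because pairing each draw with a concurrent sensor value already requires its time. It would be descriptive and could miss a drift of 2 points, so its absence from the plan is not a defect.

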PROTOCOL

Background

1. Provide the scientific background, rationale and relevance of this project.

Recent advances in continuous glucose monitors (CGMs) and availability of commercial CGM products to patients with type 1 and type 2 diabetes has made the use of CGM more widespread (1). CGMs work by placing a probe underneath the skin of a patient, into the interstitial space. The probe is an electroenzymatic sensor which uses glucose oxidase to break down glucose to create hydrogen peroxidase and other elements. Hydrogen peroxidase then interacts with a base metal layer of the sensor and is oxidized, which results in release of electrons which creates a current. The current is proportional to the glucose concentration. The current is measured by the probe and transmits a calculated glucose concentration to a receiving device (2). Substances that are widely distributed in body water, and thereby present in the interstitial space, potentially affect this technology. Acetaminophen and aspirin are substances that have been known to affect the accuracy of these devices (3); however, more recently developed CGMs such as the Dexcom G6, were able to demonstrate no interference by acetaminophen (4). Patients with end stage renal disease (ESRD) who are on intermittent hemodialysis (iHD) or peritoneal dialysis (PD) undergo fluid shifts between the interstitial fluid and intravascular space during dialysis treatments. They are also often uremic and have metabolic acidosis (5). These fluid shifts, uremia, acidosis, and volume overload (increase in interstitial fluid volume due to ESRD) have the potential to impact the performance of the most advanced and commercially available CGMs; however, use of CGM in these patients has not yet been studied (3). Moderate to severe CKD is associated with both increase in insulin resistance and decrease in insulin clearance, which results in often unpredictable and labile glucose concentrations and increased risk of hypoglycemia in these patients (6). Use of CGM, and potentially hybrid closed loop insulin delivery systems that are dependent on accurate continuous glucose monitoring, has the potential to improve glucose control and quality of life in these patients (7). We feel this study will be valuable in collecting preliminary data needed with the goal of validating the use of CGM in this patient population.

Objectives/Hypothesis

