Upon consent, the study team member will review the subject's inclusion/exclusion criteria will be assessed by the study team to ensure criteria has been met. The study team member will review the subject's medical history and medications. A serum pregnancy test will be performed for women who are of child-bearing potential. If a subject is pregnant, they will be withdrawn from the study and be advised to seek further confirmation from their primary provider. If the subject meets all criteria, they may continue with the CGM training visit on the same day or at a later date. Fingertick and *i-STAT System* blood glucose values are for study purposes only. Treatment recommendations will not be provided.

The most recent Hemoglobin A1c value that is collected for standard of care and is either dated prior to the study start date or within the data collection period if the duration between the collection date and study start date is greater than 3 months.

Day 1 (Visit 2):

Day 1 may occur on the same day as Screening. At the end of the subject's dialysis session, the study team will insert a DexCom G6 CGM sensor into the participant's abdomen and educate the subject on the use of the DexCom G6 CGM. The CGM will be blinded to both the study physician and participant during the course of study participation – there will be no visible readings during the subject's participation in the study. Selected study team members may incidentally see sensor values when downloading the CGM data. CGM supplies and CGM user's guide will be provided to the participant. Patients will be given a study glucometer, testing supplies, and a scale to measure body weight each day. They will be taught how to use the study glucometer and informed of the schedule for fingerstick monitoring that will occur during the 10 days of wearing the CGM. Subjects will also be asked to weigh themselves every morning with the study-supplied scale and record it in a study record.

Non-Dialysis Days (Days 2, 3, 7, 9, 10):

On days that the subject does not have dialysis, they will perform 7 fingerstick blood glucose tests using the study glucometer. These will be done before meals, after meals, and at bedtime. Subjects will be encouraged to use the study glucometer for any additional blood glucose values they wish to perform.

Subjects will weigh themselves every morning upon voiding and record the results in a study record.

Dialysis Days (Days 4, 6, 8, 11):

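### Study staff see i-STAT glucose live during dialysis, but the protocol bars its use for treatment without exception and gives no route for a critical value

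*Combined protocol and SAP*

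**What the plan says.** Four parts of the protocol bear on the point.

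- **Sampling.** Study Design, item 2, has a study team member take about 12 samples from the HD line per session: "These blood samples will be immediately processed using the" i-STAT. Statistical Considerations, item 2, calls the i-STAT a point-of-care machine and says that its "glucose measurements will be recorded in the study flowsheet".
- **Use of the values.** Study Procedures, Screening (Visit 1), says of fingerstick and i-STAT results that "blood glucose values are for study purposes only. Treatment recommendations will not be provided". Dialysis Days adds: "Glucose values collected during the dialysis session will not be used for treatment purposes". Neither sentence has a qualifier.
- **Care during the session.** Dialysis Days also says that the patient's run follows standard care unchanged, and that dialysis-run data, vital signs and other relevant clinical information are recorded.
- **Blinding.** Day 1 (Visit 2) hides the CGM readings from the study physician and the participant. No such rule covers the i-STAT.

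The supplied text contains no critical glucose limit and no step for passing a study glucose value to the dialysis unit.

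**The concern.** Of the two study measurements running during dialysis, the i-STAT is the only one meant to be seen live, and the person who sees it works for the study. The Background says that moderate to severe kidney disease "results in often unpredictable and labile glucose concentrations and increased risk of hypoglycemia in these patients", and Study Design, item 2, aims for about 15 insulin users. An alarming value is therefore foreseeable. A staff member who follows the text literally would enter it in the flowsheet and do nothing more. One who wants to pass it on must decide at the chairside whether two unqualified sentences allow it.

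The protocol does route one other study finding: under Screening, a participant found to be pregnant is withdrawn and advised to seek confirmation from the primary provider. A critical glucose value is more urgent and has no counterpart.

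Patient safety is the main stake. There is a lesser analytic question. Pairs taken after a treated value fall on the dialysis side of the primary hypothesis ("The MARD between CGM sensor glucose and CBG will be larger on non-HD days than during dialysis"), and the plan does not say how they are handled.

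**Working it through.** The main check is a comparison of texts; arithmetic serves only to size it. The plan states no figure on this point to reproduce.

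**Texts side by side**

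1. Samples are run at once, at the point of care, by study staff. The result is known during the session.
2. The only stated destination for the result is the study flowsheet. Nothing says that the dialysis unit sees it.
3. Screening and Dialysis Days rule out treatment use without exception.
4. Standard care continues, but no text says that the unit measures glucose at these times. It cannot act on a value that it is not given.

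Taken together, a critical value can be seen and recorded without reaching anyone responsible for the patient.

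**Exposure**

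Inputs: 30 completers (Human Participants); 10-12 samples per session (Dialysis Days); three sessions as the goal, although "two sessions will be acceptable and not considered a study deviation". The listed draw times (0, 15, 30, 45, 60, 75, 90, 120, 150 and 210 min) make 10, which agrees with the stated range.

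- Readings per patient: 10 × 2 = 20 to 12 × 3 = 36.
- Sessions: 30 × 2 = 60 to 30 × 3 = 90.
- Readings in all: 30 × 20 = 600 to 30 × 36 = 1,080.

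These readings are clustered within patients and sessions. The documents give no rate of critical values, so they do not convert to an expected number of events.

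**Reach into the analysis**

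Statistical Considerations, item 4, says that analysts will "calculate the MARD between sensor glucose and venous blood glucose for patients during hemodialysis". I assume that every i-STAT value has a paired CGM value and that all patients contribute equally.

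- Later pairs after a critical value at 0 min: 10 − 1 = 9 to 12 − 1 = 11. This is the maximum for one session.
- After one at 90 min (the seventh draw): 10 − 7 = 3 to 12 − 7 = 5.
- If every draw is equally likely to be the critical one (assumption), the mean is 4.5 to 5.5.

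| Samples × sessions | Most later pairs | Share of all dialysis pairs | Share of that patient's pairs |
|---|---|---|---|
| 10 × 2 | 9 | 9/600 = 1.50% | 9/20 = 45.0% |
| 10 × 3 | 9 | 9/900 = 1.00% | 9/30 = 30.0% |
| 12 × 2 | 11 | 11/720 = 1.53% | 11/24 = 45.8% |
| 12 × 3 | 11 | 11/1,080 = 1.02% | 11/36 = 30.6% |

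The pooled dialysis MARD with these pairs, minus the MARD without them, equals share × (their MARD − MARD of the rest). The documents give no such difference. If it were 5 to 20 percentage points (assumption), one session would move the pooled figure by 1.00% × 5 = 0.05 to 1.53% × 20 = 0.31 points at most. With the mean number of later pairs the range is 4.5/900 × 5 = 0.025 to 5.5/720 × 20 = 0.15 points.

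**The case against.** The strongest reply is that the two sentences only stop the study from directing treatment. The unit is already caring for the patient, the run follows standard care, this is not a treatment study, and nothing forbids a word to the nurse. Consent pages were not available for this review and may cover the point. The Background sentence on hypoglycemia concerns kidney disease in general and gives no in-session risk.

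Much of this stands. A reader might infer that the protocol orders staff to withhold a critical value, or that it conflicts with usual care. The documents do not support that: they bar use for treatment, not communication. What remains is that the stated rule has no exception and no supplied text gives the unit the study value. Consent wording, if there is any, would not replace an instruction beside the sentences that staff follow.

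A reader might also infer that treated sessions threaten the MARD comparison, or that all pairs after a critical value should be set aside. Neither is supported.

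- The shifts above rest on an assumed difference in MARD and are small for one session; nothing in the documents supports a count of such sessions.
- Flagging from notification, whether or not anyone treats, would select pairs by glucose level and could remove the range where accuracy matters most.
- It would also filter the dialysis side alone. No text masks the home glucometer, so participants can see and act on their own fingerstick values.
- Usual care can already produce treated pairs. The planned records, including medications (Statistical Considerations, item 5), may partly identify them, although no treatment time is specified.

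**Conclusion.** The safety gap holds as an unstated exception. The protocol has study staff obtain 20-36 live glucose readings per patient and states without qualification that those taken in dialysis will not be used for treatment. A critical value therefore need not reach the treating unit. Usual care reduces the risk but does not close the gap, because nothing in the supplied text gives the unit the value.

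This is a minor safety amendment. It rests on the supplied text alone, with consent wording unknown and the frequency of critical values not stated. No material effect on the MARD result is shown, and the plan's sample size is untouched.

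**What to change.** Keep the statement that the study gives no treatment advice. In Screening and in Dialysis Days, add an exception along these lines: any i-STAT value below a critical low limit or above a critical high limit is reported at once to the responsible clinician in the dialysis unit, who confirms it and manages it under usual care. Use the unit's own limits if it has them; otherwise the study physician sets two numbers and writes them into the protocol beforehand. Record the time of notification and the time and type of any glucose-affecting treatment with the clinical data already collected in the session.

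Keep all pairs in the primary MARD. An optional sensitivity analysis may leave out pairs from the time of an actual treatment, not from notification.

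The cost is about one paragraph of protocol text, possibly two limits to set, and a few entries in the record. No staff or samples are added. The small downside is that a few later in-session pairs may follow treatment; the recorded times would identify them.
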